The blood-to-plasma ratio of everolimus, which is concentration-dependent over the range of 5 to 5000 ng/mL, is 17% to 73%. The amount of everolimus confined to the plasma is approximately 20% at blood concentrations observed in cancer patients given everolimus 10 mg/day. Plasma protein binding is approximately 74% both in healthy subjects and in patients with moderate hepatic impairment.

Everolimus is a substrate of CYP3A4 and PgP. Following oral administration, everolimus is the main circulating component in human blood. Six main metabolites of everolimus have been detected in human blood, including three monohydroxylated metabolites, two hydrolytic ring-opened products, and a phosphatidylcholine conjugate of everolimus. These metabolites were also identified in animal species used in toxicity studies, and showed approximately 100-times less activity than everolimus itself.

In vitro, everolimus competitively inhibited the metabolism of CYP3A4 and was a mixed inhibitor of the CYP2D6 substrate dextromethorphan.

No specific elimination studies have been undertaken in cancer patients. Following the administration of a 3 mg single dose of radiolabeled everolimus in patients who were receiving cyclosporine, 80% of the radioactivity was recovered from the feces, while 5% was excreted in the urine. The parent substance was not detected in urine or feces. The mean elimination half-life of everolimus is approximately 30 hours.

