4.3.1 Patient Study Number Assignment and Sample Labeling

An additional scientific objective is to assess the pharmacodynamic effects of LEE011 and everolimus on tumor tissue and to correlate those effects to PFS. Thus, for all patients, we will require 2 core biopsies of a primary pancreatic tumor or metastatic lesion, and a third core biopsy will be optional:

- A fresh core biopsy prior to treatment (within 3 weeks of Cycle 1 Day 1)
- A repeat core biopsy on Cycle 1 Day 15 (\pm 3 days), preferably on the same tumor site if possible
- An optional final core biopsy after PD or off study, preferably on the same tumor site if possible

The first (pre-treatment) biopsy should be performed as soon as possible after consent is signed. For this reason, patients will be screened for accessibility of tumor tissue. Specifically, our radiologists will review the most recent images for each patient prior to enrollment. Only patients who, in their best estimation, have a tumor deposit(s), that are easily accessible by ultrasound or CT guidance in order to obtain serial core needle biopsies, will be eligible for study.

Patients will undergo core biopsies, as per standard protocol in the Department of Radiology. An 18-20 gauge needle will be used. At least three 1-2 cM core biopsies should be obtained with each biopsy. All samples should be labeled with the date, protocol number, protocol assigned patient number, and biopsy number (1 – pre-treatment; 2 – on-treatment; 3 – after PD or off study). The samples will be immediately placed in formalin and then embedded in paraffin.

Samples collected must be shipped at room temperature to [name] at:

Roswell Park Comprehensive Cancer Center
c/o [name]
[name]
[name]

Of note, patients who are on chronic anticoagulation will be required to hold anticoagulation prior to the biopsies being performed. Patients on warfarin must hold treatment for 5 days, but will be on low-molecular weight heparin (LMWH), 1mg/kg subcutaneously twice a day. The LMWH will continue until the last biopsy is complete. Patients may then resume warfarin the day after the last biopsy. Additionally, patients on LMWH will hold (*i.e.*, not receive) the dose of LMWH the morning of the procedure, but will resume the LMWH the evening of the day of the biopsy.

Throughout the study, the following labelling procedures will be followed

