4.4 Detailed Patient Assessments

Subject assessments (physical examinations, vital signs, performance status, chemistry, hematology, medication review, and adverse event evaluations) will be conducted at screening, Cycle 1 Day 1, every 2 weeks thereafter until the first response assessment at 8 weeks, and then every 4 weeks thereafter. Study visits and the on-treatment tumor biopsy may be performed 3 days before or after the scheduled date due to unforeseen or unavoidable circumstances, and attempts should be made to schedule visits to line up with the start of a new cycle (within the constraints of the above parameters). Study drugs will be dispensed at the last visit prior to the start of the next 28 day cycle. The radiologic first response assessment at 8 weeks, and subsequent radiologic response assessments every 8 weeks thereafter, may be performed up to 7 days before or after the scheduled date due to unforeseen or unavoidable circumstances. Details are provided in Table 5, and a checklist highlighting the important events for screening through the completion of the trial is provided below, as Table 6.

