	Grade 3 laboratory abnormalities that are responsive to oral supplementation or deemed by the investigator to be clinically insignificant

6.7.1.2 Dose reduction and delays due to toxicities related to known toxicities of LEE011 or everolimus

If a subject experiences a DLT, as defined above in Table 10, the subject will complete the planned activities of the cycle as scheduled (*i.e.*, CT scans and lab tests will be performed per standard of care). The following are guidelines for dose delay and discontinuation of the study drugs:

- 1) All treatment drugs should be discontinued/delayed concurrently until the toxicity resolves to Grade 1 or lower or to baseline if Grade 2 at the time of study entry.

- a. Of note, LEE011 is known to be associated with myelosuppression. Thus, for Grade 2 or 3 neutropenia, anemia, or thrombocytopenia which do NOT meet the definition of a DLT as detailed in Table 10, then treatment will continue without modification.
 - i. Patients who experience Grade 2 or 3 neutropenia, anemia, or thrombocytopenia, while continuing treatment without modification for that cycle, will be followed with weekly CBCs to track the recovery (or worsening) of the myelosuppression
 - ii. Dose modifications for Grade 2 or 3 neutropenia, anemia, or thrombocytopenia as detailed in Table 11 below will then be instituted FOR SUBSEQUENT CYCLES of therapy
 1. Thus, for example, a patient who experiences Grade 3 thrombocytopenia without bleeding at Cycle 1, Day 15 will continue treatment without modification. CBCs will be checked weekly
 - a. If the thrombocytopenia worsens to Grade 4, for example Cycle 1, Day 22, then treatment will be held, and dose reductions will be instituted starting Cycle 2
 - b. If the thrombocytopenia does NOT worsen through Cycle 1, then treatment hold and dose modifications will be followed for Cycle 2, as per Table 11 below
 - iii. For clarity, for any hematologic toxicity that meets the definition of a DLT (even in the Phase II portion), treatment will be held, and doses modified as per Table 11, even within a cycle.
- 2) Subjects may delay retreatment for up to 3 weeks to allow the toxicity to resolve. In the Phase II portion of the study, dose adjustments will be followed, as per Table 11. One dose adjustment is allowed, as delineated in Table 11.

Table 11. Dose Modifications for Toxicities Related to LEE011 or everolimus

Hematologic	
Thrombocytopenia	
Grade 1 ($\geq 75 \times 10^9/L$)	No dose adjustment required

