8.0 CORRELATIVE RESEARCH AND TUMOR BIOPSIES

8.1 Pharmacodynamic Assessment of the Efficacy of LEE011 and Everolimus

8.1.1 Introduction

The primary objective of this trial is to determine the efficacy of LEE011 and everolimus in patients with refractory mPAC. However, an important secondary endpoint is to assess the pharmacodynamic effects of the combination treatment on cell cycle, the retinoblastoma pathways and MTOR pathways, and to correlate those effects to the PFS. Thus, for all patients, we will require at least 2 serial biopsies.

- A fresh biopsy prior to treatment
- A repeat biopsy on the Cycle 1 Day 15
- An optional final biopsy after PD or off study

The first (pre-treatment) biopsy should be performed as soon as possible after consent is signed. For this reason, patients will be screened for accessibility of tumor tissue. Specifically, our radiologists will review the most recent images for each patient prior to enrollment. Only patients who, in their best estimation, have a tumor deposit(s), that are easily accessible by ultrasound or CT guidance in order to obtain serial core needle biopsies, will be eligible for study

With regards to the timing of the second biopsy, the pharmacokinetics of both LEE011 and everolimus suggest that the LEE011 reaches steady state by Day 8, and the everolimus by 2 weeks. Thus, the second biopsy was requested at a time point wherein both agents have achieved steady state, but before the week off of LEE011.

Patients will undergo core biopsies, as per standard protocol in the Department of Radiology. An 18-20 gauge needle will be used. At least four 1-2 cM core biopsies should be obtained with each biopsy. All samples should be labeled with the date, protocol number, protocol assigned patient number, and biopsy number (1 – pre-treatment; 2 – on-treatment; 3 – after PD or off study).

2 cores should be placed in screw-top tubes and frozen in liquid nitrogen.

The other 2 cores should be immediately placed in formalin and then embedded in paraffin.

Throughout the study, the following labeling procedures will be followed

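### The second biopsy is scheduled by calendar, so a patient on a dose hold may be sampled off drug and still be analysed as on-treatment

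*Combined protocol and SAP*

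**What the plan says.** **Rationale.** Section 8.1.1 says LEE011 reaches steady state by Day 8 and everolimus by two weeks, and concludes: "Thus, the second biopsy was requested at a time point wherein both agents have achieved steady state, but before the week off of LEE011". That holds only for a patient who is taking both drugs.

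**Schedule.** Section 4.3.1 asks for "A repeat core biopsy on Cycle 1 Day 15", with a margin of three days. Section 8.1.1 repeats the day, and Table 7 marks a biopsy in that column. Section 4.4 describes the margin: "Study visits and the on-treatment tumor biopsy may be performed 3 days before or after the scheduled date due to unforeseen or unavoidable circumstances". The margin is not linked to dosing. The only exception to the mandatory biopsy is a judgement, made with radiology, that attempting it would be too risky (3.2 and 4.3).

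**Holds.** Section 6.7.1.2 states: "All treatment drugs should be discontinued/delayed concurrently until the toxicity resolves to Grade 1 or lower" (or to baseline, if that was Grade 2). It adds: "Subjects may delay retreatment for up to 3 weeks to allow the toxicity to resolve". Table 11 holds both drugs for, among other things, a Grade 2 reaction in its category of other adverse reactions, a Grade 2 bilirubin rise, and a rise in AST or ALT to Grade 2. After a DLT, "the subject will complete the planned activities of the cycle as scheduled"; the text in brackets that follows mentions CT scans and laboratory tests.

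**Analysis.** Section 9.4.2.5 compares marker expression in the pre-treatment and on-treatment biopsies. Section 9.5.2.3 expects falls in proliferation markers and fits Cox models of markers against PFS. Neither defines an evaluable set or a minimum of dosing before the second biopsy.

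**The concern.** The plan states what makes the second sample valid but enforces it neither when the sample is taken nor when it is analysed. If both drugs have been on hold for several days, a Day 15 sample does not show the effect of the combination at steady state, yet it carries the on-treatment code.

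Three things are at stake:

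- **The estimated change.** Off-drug samples pooled with on-drug ones pull the mean change in pRB, pS6, Ki67 and MCM7 towards zero.
- **The marker-PFS models.** An unchanged marker would partly mean that treatment had been interrupted for toxicity.
- **The patient.** A core biopsy taken off drug carries procedural risk, and an interruption of anticoagulation for some patients (4.3.1), without answering the question it is taken for.

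**Working it through.** **1. The plan's own powered figure.** The documents give no power, effect size or SD for the pharmacodynamic comparison. The only powered figure is the Phase II design in 9.3 and 9.5.1: continue with at least 3 of 11, success with at least 10 of 26. The exact probability P(X1 ≥ 3 and X1 + X2 ≥ 10) is 0.0857 at a rate of 25% and 0.9005 at 50%. This agrees with the stated one-sided 0.1 and 90% power. Biopsy timing does not enter the calculation.

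**2. Can a hold cover the biopsy?** The window runs from Day 12 to Day 18 (15 − 3 to 15 + 3). A hold may last up to three weeks. A hold that starts before Day 15 can therefore span the whole window. A hold that starts at the Day 15 visit can be three days old at a Day 18 biopsy.

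**3. Everolimus left after a hold.** Section 1.4.3: "The mean elimination half-life of everolimus is approximately 30 hours". Fraction remaining = 0.5^(hours off / 30).

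| Days off | Exponent | Remaining |
|---|---|---|
| 1 | 24/30 | 57% |
| 2 | 48/30 | 33% |
| 3 | 72/30 | 19% |
| 5 | 120/30 | 6% |
| 7 | 168/30 | 2% |

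The corresponding LEE011 section is redacted, so no such figure can be given for LEE011. A half-life is also not a marker recovery time, which the documents do not give.

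**4. Effect of pooling (illustration).** These inputs are assumptions, not figures from the plan:
- 26 pairs, and a two-sided paired t-test at 0.05.
- A standardised change d = 0.572, which gives 80% power when every pair is on drug.
- A share h of pairs sampled off drug with no marker effect at all, which is the worst case.

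The mean change becomes (1 − h)d, and the variance of the change becomes 1 + h(1 − h)d². For h = 0.10 the mean is 0.9 × 0.572 = 0.515, the SD is √(1 + 0.09 × 0.327) = 1.015, and the standardised change is 0.507.

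| h | Mean change kept | Power, all pairs | Pairs left if excluded | Power, excluded |
|---|---|---|---|---|
| 5% | 95% | 75% | 25 | 78% |
| 10% | 90% | 70% | 23 | 75% |
| 20% | 80% | 59% | 21 | 70% |
| 30% | 70% | 48% | 18 | 63% |

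With 20 pairs (d = 0.66 for 80% power) the results are similar: 75% against 78% at h = 5%, and 70% against 75% at h = 10%.

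**5. Which rows are plausible?** Three features of the plan point to the top of the table:
- The first scheduled visit after Day 1 is Day 15 (4.4), so holds triggered by laboratory tests or ECG would mostly begin on the biopsy day. A same-day biopsy is little affected.
- Grade 2-3 cytopenias that are not DLTs do not stop drug within the cycle (6.7.1.2).
- What mainly remains is symptomatic toxicity reported before Day 15, plus biopsies taken late in the window after a hold begins at the visit.

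**The case against.** A reader might infer that patients on hold are in fact biopsied off drug. The documents do not say so. The sentence about completing planned activities applies only to DLTs and does not name biopsies. For other holds nothing is said. The synopsis and 4.1.2 place the second biopsy two weeks into treatment, and a site could take that to require current dosing. This objection stands to the extent that off-drug sampling is a possibility the plan leaves open, not an instruction. The gap remains, because the biopsy is a scheduled Day 15 activity and no text suspends it.

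A reader might also infer a loss of 10-30% of the effect, with power falling to about one half. That does not stand as an estimate. The hold rate, the effect size, the number of pairs and the absence of any off-drug effect are all assumed. Biopsies are required of Phase I patients too, with some exempted, so 26 is not the plan's number of pairs.

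Two further points are fair. The diary (5.1) records the date and time of each dose and samples carry a date, so off-drug samples can be identified and dilution arises only if they are pooled. Restricting the marker-PFS models to on-drug pairs also has a cost: it selects patients who tolerate treatment.

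**Conclusion.** The point holds in a limited form. A calendar rule with no dosing condition conflicts with the steady-state rationale in 8.1.1, and the analysis sections do not separate samples taken during a hold. The number of patients affected cannot be derived from the documents and is probably small. At h = 5-10% the mean change shrinks by 5-10%, and pooling costs about 3 to 5 points of power compared with excluding those pairs. Both figures rest on the worst-case assumption of no marker effect off drug.

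The consequence is confined to the pharmacodynamic work, which 9.5.2.3 calls exploratory and 8.1.1 treats as an important secondary aim. PFS at 8 weeks, its sample size and its decision rules are unaffected. The change is still worth making: it is cheap, and it avoids an invasive procedure that cannot serve its stated purpose.

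**What to change.** 1. **Sections 4.3.1 and 8.1.1.** Reconcile the calendar schedule with the steady-state rationale. State that the second biopsy is deferred or omitted when the drugs are on hold. The investigators should set the dosing interval required beforehand and allow for an isolated missed dose, which 5.1 anticipates. No dose or hold rule needs to change for this.
2. **Sections 9.4.2.5 and 9.5.2.3.** Define a pharmacodynamic-evaluable set from the diary and the biopsy dates. Base the comparison of the two biopsies on that set and list off-drug samples separately. Report the marker-PFS models both in that set and in all pairs, because the restriction selects for tolerability.

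**Cost.** Protocol wording and a derived variable from records already kept, with no added procedure. A few biopsies will be lost or taken at a later time point. Some will be taken at a lower LEE011 dose level, where Table 11 restarts the patient one level down, so the time point and dose level should be shown with the results.

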8.1.1.1 Patient Study Number Assignment

Patients will be de-identified and labeled with a 5 digit study label (X-XXX-X):

- The first number will be the site from which the patient was enrolled (single digit)
 - o 1 = Georgetown
- The second number will be the site-assigned patient number (three digit)
- The third number will indicate the collection timing
 - o 1 = Pre-treatment
 - o 2 = On treatment

8.1.1.2 Labeling of Serial Blood Samples

Serial blood samples will be labeled in a similar fashion, except that the collection timing will be labeled by week number (e.g. week 0 = pretreatment; week 8; week 16)

8.1.1.3 Sample Shipment

Samples collected must be shipped at room temperature to [name] at:

Roswell Park Comprehensive Cancer Center
c/o [name]
[name]
[name]

8.1.2 Assessment of Pharmacodynamic Effects of LEE011 and Everolimus

A formalin-fixed, paraffin embedded core sample from the pre-treatment and on-treatment tumor biopsies will be used to make slides to stain for the following markers by IHC with the indicated cutpoints:

- a. RB, defined as negative if tumor cells are devoid of nuclear staining, while lymphocytes and stromal cells have positive nuclear staining.
- b. pRB (phosphorylated Ser780), defined using a histoscore of intensity and percent of tumor cell nuclei staining.
- c. p16 levels are defined using established clinical staining criteria (0-3+)
- d. Cyclin D1, defined using intensity and predominant localization (nuclear/cytoplasmic)
- e. Ki67, defined as a percentage of positively stained nuclei in the tumor compartment
- f. MCM7, defined as a percentage of positively stained cells nuclei in the tumor compartment
- g. pS6 (Ser235/236) defined using a histoscore of intensity and percent of tumor cells staining

LEE011 directly suppresses the phosphorylation of RB which provides an assessment of on-target activity. Ki67 and MCM7 are markers of proliferation and are expected to diminish with treatment associated with response. RB, Cyclin D1, and p16 could be predictive markers of response, and the absence of RB and high-levels of p16 are associated with resistance. Phosphorylation of s6 protein is mediated by MTOR and provides a marker for the efficacy of MTOR inhibition by everolimus.

8.2 Mutational Analysis of Tumor Samples

Pre-treatment biopsy samples will be used for targeted next generation sequencing using a panel that includes 196 genes commonly altered in cancer with a specific emphasis on genes that are altered in pancreatic cancer. This platform will allow >500x coverage across the genes and provide both single nucleotide variant and copy number information. Each common gene mutation will be evaluated for association with PFS. The presence of a *CDKN2A* mutation or deletion will be correlated with PFS, given the hypothesis that derangement in this pathway results in p16 loss, creating a therapeutic target of CDK4/6 (naturally inhibited by p16).

8.3 Analysis of ctDNA

ctDNA will be collected from patient serum at Cycle 1 Day 1 and every 8 weeks thereafter. Mutations identified by the targeted sequencing will be evaluated in the circulating DNA specimens using PCR (predominantly focused around KRAS, TP53, or *CDKN2A* mutations). We will correlate changes in the ctDNA abundance with PFS and tumor marker levels. The data will determine if ctDNA may be a possible surrogate marker for disease burden.

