4.4.4 Clinical Laboratory Tests

All subjects will undergo the laboratory assessments outlined in Table 5.

- 1) A complete blood count (CBC) with differential will be collected at the screening visit, on Cycle 1 Day 1, Cycle 1 Day 15, then every 2 weeks until the first response assessment, at the first response assessment at 8 weeks, then every 4 weeks thereafter.
- 2) Serum chemistries (total protein, albumin, total bilirubin, AST, ALT, alkaline phosphatase, sodium, potassium, chloride, bicarbonate, BUN, creatinine, calcium, magnesium, and phosphorous) will be collected at the screening visit, on Cycle 1 Day 1, Cycle 1 Day 15, then every 2 weeks until the first response assessment, at the first response assessment at 8 weeks, then every 4 weeks thereafter.
- 3) PT/PTT/INR will be collected at the screening visit, on Cycle 1 Day 15, and at final visit if the patient agrees to the optional third biopsy
- 4) Additionally, a tumor marker (serum CA19-9 or CEA level) and research blood samples for ctDNA will be sampled on Cycle 1 Day 1 and every 8 weeks thereafter.

Laboratory samples for this study will be assessed using the certified laboratory at the investigators' institutions, or at a clinical laboratory such as Quest or LabCorp and these data will

be used for all data analysis. The Principal Investigator or sub-investigator will review, initial and date all laboratory results. Any laboratory value outside the reference range that is considered clinically significant by the investigator will be followed as appropriate. Clinically significant laboratory values will be recorded as adverse events if they meet the criteria as specified in Section 8.

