7.2.3 Baseline Documentation of "Target" and "Non-Target" Lesions

All measurable lesions up to a maximum of 2 lesions per organ and 5 lesions in total, representative of all involved organs should be identified as target lesions and recorded and measured at baseline. Target lesions should be selected on the basis of their size (lesions with the longest diameter) and their suitability for accurate repeated measurements (either by imaging techniques or clinically). A sum of the longest diameter (LD) for all target lesions will be calculated and reported as the baseline sum LD. The baseline sum LD will be used as reference by which to characterize the objective tumor response. All other lesions (or sites of disease) should be identified as non-target lesions and should also be recorded at baseline. Measurements of these lesions are not required, but the presence or absence of each should be noted throughout follow-up.

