9.1.4 Exploratory Objectives

9.1.4.1 To correlate the PFS_{8 weeks} to correlative scientific markers, including the analysis of tumor biopsies and blood-based markers, including RB, pRB, p16, cyclin D1, Ki67, MCM7, and pS6 levels by immunohistochemistry

9.1.4.2 To screen for use a targeted sequencing approach for genetic lesions observed in pancreatic cancer that includes KRAS, SMAD4, TP53, CDKN2A as well as other commonly mutated cancer genes

9.1.4.1 To assess blood for the analysis of circulating tumor DNA as a surrogate marker of disease burden. KRAS and other mutations will be used as the determinants of tumor selective DNA

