9.5.2 Analytic plan for secondary objectives

9.5.2.1 Survival and response endpoints:

9.5.2.1.1 The nonparametric Kaplan-Meier method will be used to estimate median PFS.

9.5.2.1.2 The nonparametric Kaplan-Meier method will be used to estimate median OS.

9.5.2.1.3 We plan to determine the ORR within a $\pm 20\%$ range based on our sample size.

9.5.2.2 Adverse event data will be compiled and tabulated using descriptive statistics.

9.5.2.3 Pharmacodynamic analyses are exploratory, but we hypothesize that proliferation indices (Ki67 and MCM7) will be decreased in the on-treatment sample compared to the pre-treatment sample and could correlate with PFS. Similarly, expected decreases in levels of pRB, cyclin D1, p16, and increases in RB could correlate with PFS. Cox proportional hazard regression models will be fit to determine whether these secondary endpoints are associated with PFS.

9.5.2.4 NGS analysis is also exploratory in nature. Using results from these analyses will examine whether median PFS is different with patients with mutations in *CDKN2A* compared to those without these mutations.

9.5.2.5 ctDNA studies are exploratory and overall trends in serial measurements may support a response (or lack of response) signal to treatment and could be correlated with PFS as a surrogate marker of disease burden.

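### ctDNA is to be judged as a surrogate for disease burden, but it is compared with PFS and CA 19-9/CEA and never with the imaging tumor burden collected on the same 8-week schedule

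*Combined protocol and SAP*

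**What the plan says.** The aim is stated consistently. Section 9.1.4 (and likewise 2.3.3) gives the exploratory objective: "To assess blood for the analysis of circulating tumor DNA as a surrogate marker of disease burden". Section 8.3 repeats it: "The data will determine if ctDNA may be a possible surrogate marker for disease burden".

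The planned comparisons are these:

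- Section 8.3: "We will correlate changes in the ctDNA abundance with PFS and tumor marker levels".
- Section 9.5.2.5: "ctDNA studies are exploratory and overall trends in serial measurements may support a response (or lack of response) signal", after which ctDNA "could be correlated with PFS as a surrogate marker of disease burden". No variable, test or model is given for the trends.

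The plan also collects a size measure. Section 7.2.3 says: "A sum of the longest diameter (LD) for all target lesions will be calculated and reported as the baseline sum LD", and "The baseline sum LD will be used as reference by which to characterize the objective tumor response". Sections 7.2.4.2 to 7.2.4.4 need the same sum at each later assessment to separate PR, SD and PD.

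The schedules coincide on paper. Section 4.4.4 says that "research blood samples for ctDNA will be sampled on Cycle 1 Day 1 and every 8 weeks thereafter", and section 4.4.8 puts response imaging every 8 weeks. The Table 8 checklist lists both at the first response assessment and at each 8-week assessment after it.

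**The concern.** A surrogate for disease burden should be checked against disease burden. Neither named comparator measures it directly. PFS is a time-to-event outcome, so an association with it shows that ctDNA change is prognostic, which is a different property. CA 19-9/CEA bears on burden but is itself a blood marker, so agreement between it and ctDNA is agreement between two indirect measures.

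At stake is how the exploratory objective is read at the end. An assay that follows tumor size closely but predicts progression weakly would look poor under the written plan. One that is prognostic for reasons other than tumor size would look like a burden marker.

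**Working it through.** **1. Aim against comparator.**

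| Comparator | Where named for ctDNA | What an association shows |
|---|---|---|
| PFS | 8.3, 9.5.2.5 | Prognostic value |
| CA 19-9/CEA | 8.3 | Agreement with another indirect marker |
| Overall trends and response signal | 9.5.2.5 | Unspecified |
| Sum of longest diameters | Nowhere | Agreement with measured target-lesion burden |

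**2. How far PFS departs from target-lesion size.** Section 7.2.4.3 counts new lesions and non-target progression as PD. Section 7.4 adds investigator-determined clinical progression, such as ECOG decline or a need for palliative treatment. Section 9.4.2.1 lists death from any cause as an endpoint and then censors patients who die on study.

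**3. The plan's own figure.** The only powered figure is the Phase II sample size. With 11 then 26 patients, continuing at 3 or more and succeeding at 10 or more:

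P(success) = Σ over x = 3 to 11 of b(x; 11, p) × P(Bin(15, p) ≥ 10 − x)

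This gives 0.0857 at p = 0.25 and 0.9005 at p = 0.50, so the design reproduces. No power is stated for ctDNA.

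**4. What 26 patients allow against the sum of diameters.** Assume two-sided 0.05 and one baseline-to-week-8 pair per patient. Fisher z power ≈ Φ(√(n − 3) × atanh(ρ) − 1.96). For n = 26 and ρ = 0.5: √23 × 0.549 = 2.63, and Φ(0.67) = 0.75.

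| Pairs | ρ = 0.4 | ρ = 0.5 | ρ = 0.6 |
|---|---|---|---|
| 26 | 0.53 | 0.75 | 0.91 |
| 22 | 0.46 | 0.67 | 0.86 |
| 18 | 0.38 | 0.57 | 0.77 |

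The documents give neither ρ nor the number of pairs.

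**5. PFS after week 8.** A ctDNA change from baseline first exists at week 8, when the first scan is read. A PFS analysis that starts there keeps 26 × 0.25 = 6.5 patients under the null rate or 26 × 0.50 = 13 under the alternative. At ρ = 0.5, Fisher z power is then 0.20 (n = 7) or 0.41 (n = 13).

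**6. Is PFS in general the weaker comparator?** Simulation: N = 26, 80% with a paired week-8 sample and scan, Spearman test at two-sided 0.05, 3000 runs. Log change in the sum of diameters is N(0.18, 0.25). PD occurs if that change exceeds 0.18 (log 1.2 = 0.18) or by a new lesion in 25% of patients, so 1 − 0.5 × 0.75 = 62.5% progress at the first scan. The hazard of later progression is also assumed. Entries are power for PFS / power for the sum of diameters.

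| True ρ (ctDNA change, size change) | ctDNA blind to new lesions | New lesion adds 1 SD of burden | New lesion adds 2 SD |
|---|---|---|---|
| 0.5 | 28% / 60% | 39% / 51% | 38% / 34% |
| 0.6 | 39% / 79% | 54% / 70% | 56% / 50% |
| 0.7 | 52% / 92% | 71% / 86% | 74% / 65% |

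A separate build of the model at ρ = 0.6 gave 37% / 77%, 51% / 69% and 52% / 51%. The advantage over PFS shrinks, and then disappears or reverses, as ctDNA reflects new lesions.

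**7. CA 19-9/CEA.** The number of pairs is the same as for the sum of diameters. If the marker is tied to ctDNA only through burden, simulated power at ρ = 0.6 with n = 26 is 0.20, 0.40, 0.65 and 0.78 for marker-burden correlations of 0.4, 0.6, 0.8 and 0.9, against 0.88 for the sum of diameters. If the marker correlates with ctDNA as strongly as size does, power is equal.

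**The case against.** The strongest reply has four parts.

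- **Status.** The work is labelled exploratory and has no test, threshold or decision rule. A reader might infer that the plan will wrongly accept or reject ctDNA as a surrogate, but nothing in it commits to such a verdict. This stands, and it limits the point to one of interpretation.
- **Sum of diameters is not burden either.** Section 7.2.3 caps target lesions at five, two per organ, and leaves non-target disease unmeasured. Section 7.2.1.3 classes ascites, effusions and bone lesions as non-measurable, and new lesions fall outside the sum. PFS does pick up new and non-target disease. This stands: the sum should be the main comparator but not the only evidence.
- **Response is already mentioned.** Section 9.5.2.5 looks for a response signal in ctDNA trends, and RECIST response rests on the sum of diameters. This stands only in part: no variable or statistic is named, and a response category is coarser than the measured size.
- **Power.** A reader might infer that the written plan has much less power. The documents give no such figure. Steps 6 and 7 show that the comparison with PFS depends on whether ctDNA reflects new lesions, and that no general loss is shown for CA 19-9/CEA. Taking 26 as the sample is itself a simplification, since the synopsis allows up to 44 evaluable patients. Nor is PFS read purely on an 8-week grid, because section 7.4 admits clinical progression and visits are every 2 weeks up to week 8.

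**Conclusion.** The point holds as a mismatch between objective and analysis. PFS answers a prognostic question, CA 19-9/CEA gives indirect support, and the imaging measure already collected is not used for ctDNA in either section. This rests on the text and needs no simulation.

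Its size is small. The analysis is exploratory, the primary endpoint and sample size are untouched, and no stated figure changes. A general power claim is not supported. The power figures rest on assumed correlations, pair counts, progression patterns and a two-sided 0.05 level that the plan does not state. The loss is clearest for PFS analysed from week 8, where few patients remain.

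Matching is approximate. The baseline scan may precede Cycle 1 Day 1 by up to 3 weeks (4.4.8), and later scans have a 7-day window either side (4.4). Table 7, as read from the PDF, marks ctDNA under the 4-weekly column and not at the first response assessment, unlike 4.4.4 and Table 8. That may be an extraction fault, but it should be confirmed because the week-8 pair depends on it.

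**What to change.** In 8.3 and 9.5.2.5:

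1. Make the main surrogacy analysis the association of log ctDNA with the RECIST sum of longest diameters at matched assessments, for levels and for changes from baseline. Use Spearman correlation or a repeated-measures mixed model, and state the matching window.
2. Report new-lesion and non-target progression status alongside, because the sum covers at most five target lesions.
3. Keep CA 19-9/CEA as supportive evidence.
4. Report ctDNA against PFS as a separate prognostic analysis, from a week-8 landmark when the week-8 change is the predictor, and do not use it to conclude on disease burden.

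The cost is analysis-plan wording. The sum is already needed at each response assessment, so no patients, samples or scans are added.
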